## Study Information

Title	Assessment of overall survival in Medicare patients with HR+/HER2- metastatic breast cancer treated with palbociclib
Protocol number	A5481182
Protocol version identifier	1.0
Date	Version 1.0: 6 September 2023
Active substance	Palbociclib
Medicinal product	Ibrance
Research question and objectives	
The primary objective of this study is:
 

• To compare overall survival (OS) of first-line palbociclib + aromatase inhibitor (AI) versus AI alone for women or men with HR+/HER2- de novo metastatic breast cancer (mBC) in the SEER-Medicare data

Authors	
RTI Health Solutions: PPD
  
Pfizer: PPD
  
Please refer to Section 3 Responsible Parties for detailed author affiliation and contact details.

PFIZER CONFIDENTIAL

## 2 LIST OF ABBREVIATIONS

Abbreviation	Term
1L	first line
2L	second line
ACS	American Community Survey
AI	aromatase inhibitor
AJCC	American Joint Committee on Cancer
CDK4/6	cyclin-dependent kinase 4 and 6
CFR	Code of Federal Regulations
CI	confidence interval
CPH	Cox proportional hazards
EOD	Extent of Disease
ER	estrogen receptor
ET	endocrine therapy
HCPCS	Healthcare Common Procedure Coding System
HER2	human epidermal growth factor receptor 2
HER2-	human epidermal growth factor receptor 2-negative
HMO	health maintenance organization
HR+	hormone receptor-positive
IEC	independent ethics committee
IPTW	inverse probability of treatment weighting
IRB	institutional review board
LIS	low-income subsidy
mBC	metastatic breast cancer
N/A	not applicable
NAACCR	North American Association of Central Cancer Registries
NCI	National Cancer Institute
NCICI	National Cancer Institute Comorbidity Index
NHIA	NAACCR Hispanic Identification Algorithm
NOS	not otherwise specified
OQ	Office of Quality
OS	overall survival

PFIZER CONFIDENTIAL

Abbreviation	Term
CCI	
PR	progesterone receptor
PS	propensity score
PSM	propensity score matching
RPSFT	Rank Preserving Structural Failure Time
RTI-HS	RTI Health Solutions
SEER	Surveillance, Epidemiology, and End Results
sIPTW	stabilized inverse probability of treatment weighting
SSA	Social Security Administration
CCI	
US	United States

PFIZER CONFIDENTIAL

## 4 ABSTRACT

Not applicable.

## 5 AMENDMENTS AND UPDATES

Amendment number	Date	Protocol section(s) changed	Summary of amendment(s)	Reason

## 6 MILESTONES

Milestone	Planned date/anticipated timeline
Kickoff meeting	3 May 2023
Acquire study data	Quarter 3, 2023
Final study protocol	Quarter 3, 2023
Data analysis	Quarter 2, 2024
Prepare study report	Quarter 4, 2024

PFIZER CONFIDENTIAL

## 7 RATIONALE AND BACKGROUND

Nearly 70% of all metastatic breast cancer (mBC) cases are of the hormone receptor-positive (HR+)/human epidermal growth factor receptor 2-negative (HER2-) subtype. Endocrine therapies (ETs), such as aromatase inhibitors (AIs), tamoxifen, and fulvestrant, have remained the mainstay of therapy for patients with HR+/HER2- mBC for nearly 2 decades; however, in recent years, several newer targeted therapies, particularly the class of cyclin-dependent kinase 4 and 6 (CDK4/6) inhibitors, have become available: palbociclib (February 2015), ribociclib (March 2017), and abemaciclib (September 2017). Phase 3 clinical studies have shown that CDK4/6 inhibitors used in combination with an AI in first line (1L) in HR+/HER2- mBC significantly increased progression-free survival compared with AI monotherapy. However, evidence on the secondary endpoint of overall survival (OS) from the clinical studies is mixed across different CDK4/6 inhibitors. In the phase 3 trial PALOMA-2, palbociclib + letrozole in the 1L setting demonstrated a numerical improvement but not a statistically significant OS increase, with median OS of 53.9 months for palbociclib + letrozole versus 51.2 months for letrozole alone (hazard ratio, 0.956; 95% confidence interval [CI], 0.78-1.18) (Finn et al., 2022). Likewise, in PALOMA-3, treatment with palbociclib + fulvestrant, after progression or relapse during previous ET, yielded a clinically important but not statistically significant survival improvement over fulvestrant monotherapy (median OS, 39.7 vs. 29.7 months; hazard ratio, 0.81; 95% CI, 0.64-1.03) (Turner et al., 2018). In a post hoc analysis of PALOMA trials, time to chemotherapy initiation was considerably longer for patients treated with palbociclib + letrozole (in PALOMA-2) and palbociclib + fulvestrant (in PALOMA-3) versus the respective non-palbociclib control groups (Rugo et al., 2022b). Further, an exploratory analysis of PALOMA-3 trial patients showed that patients who had not been treated with a prior chemotherapy for advanced breast cancer had improved OS with the palbociclib combination therapy versus the control group (median OS, 39.7 vs. 29.5 months; hazard ratio, 0.75; 95% CI, 0.56-1.01) (Rugo et al., 2021).

Data from at least 2 observational studies have shown possible OS benefits in relatively older patient populations. Results from P-Reality-X, a real-world evidence study conducted using data from the Flatiron electronic health record (median age, 70 years for palbociclib treatment group), also reported improved OS, specifically for patients receiving palbociclib + AI compared with AI alone. After stabilized inverse probability treatment weighting, median OS (95% CI) is significantly longer among palbociclib compared with AI recipients (49.1 [45.2-57.7] vs. 43.2 [37.6-48.0] months; hazard ratio, 0.76 [95% CI, 0.65-0.87];  $P < 0.0001$ ) (Rugo et al., 2022a). In another study of older patients (median age, 74 years for both the treatment arms: palbociclib + letrozole and letrozole alone), the palbociclib group was shown to have significantly better OS than the letrozole alone group (hazard ratio, 0.55 [95% CI, 0.42-0.72];  $P < 0.001$ ) (Rugo et al., 2023). In a recent observational study of an Medicare population of patients with diagnosis of de novo HR+/HER2- mBC using data from the Surveillance, Epidemiology, and End Results (SEER)-Medicare during an early period of CDK4/6 inhibitors use (2015-2017), Goyal et al. (2023) analyzed the effect of the CDK4/6 inhibitors (as a class) on OS and reported that combination therapy with ET and a CDK4/6 inhibitor is independently associated with improved OS compared with ET alone (hazard ratio, 0.59; 95% CI, 0.42-0.82). The majority ( $\geq 90\%$ )

PFIZER CONFIDENTIAL

of patients in the CDK4/6 inhibitor group (median age, 70 years) in this study were taking palbociclib ([Trapani and Mayer, 2023](#)).

Because the evidence from real-world populations are often underrepresented in clinical trials ([Lewis et al., 2003](#); [Loree et al., 2019](#); [Murthy et al., 2004](#); [Talarico et al., 2004](#)), and because 2 additional years of SEER-Medicare data have now become available allowing for more sample size and additional follow-up we seek to understand current data on potential survival benefits among the primary cohort of patients treated with palbociclib + AI compared with AI alone after de novo mBC diagnosis. A description of the SEER-Medicare database is provided in Section [9.4](#).

## 8 OBJECTIVES AND RESEARCH QUESTIONS

[figure not shown]
Following the work of [Goyal et al. \(2023\)](#), this retrospective, noninterventional study aims to assess OS in Medicare patients with HR+/HER2- de novo mBC who initiated 1L treatment with palbociclib + AI combination therapy versus AI alone. Specifically, the key objectives of this study are as follows:

### Primary objective:

- To compare OS of 1L palbociclib + AI versus AI alone for women or men with de novo HR+/HER2- mBC in the SEER-Medicare database who are  $\geq 65$  years old

### Exploratory objectives:

CCI

- To measure time to chemotherapy, if enough follow-up time is available to assess this measure.

## 9 RESEARCH METHODS

### 9.1 Study Design

This study will encompass a retrospective cohort analysis using clinical and administrative claims data from the linked SEER-Medicare database (providing SEER data are available through 2019 and linked Medicare claims are available through 2020) for patients with diagnosis of HR+/HER2- mBC at initial presentation. The study will assess the rates of OS in patients 65 years or older with diagnosis of de novo mBC from 2015-2019 who initiated 1L systemic therapy with palbociclib + AI

[figure not shown]
PFIZER CONFIDENTIAL

or AI alone following the first approval of palbociclib in February 2015. [Figure 1](#) presents a graphical schema of the study design (drawn for a hypothetical patient and not to scale).

Based on the study schema presented below, the following key study definitions will apply:

- **De novo mBC diagnosis date window:** From 1 February 2015 through 31 December 2019.
- **Study index date:** The date of 1L treatment initiation with palbociclib + AI or AI alone after the de novo mBC diagnosis.
- **Case selection window (index period):** From 1 February 2015 through 30 June 2020 for the date of 1L treatment initiation (study index date).
- **Baseline period:** The 6-month period before the study index date (to assess patient baseline demographic and clinical characteristics).
- **Study follow-up:** All patients will be followed from their study index date through the earliest of the following: death, disenrollment from Medicare Part A (hospital insurance), Part B (medical insurance), or Part D (prescription drug insurance), enrollment in a health maintenance organization (HMO) plan, or end of the study database (31 December 2020).
- **Overall study period:** From 1 August 2014 (to allow up to 6 months of look-back period for any patient with an index date in February 2015) through 31 December 2020 (accounting for a minimum 6 months of potential follow-up for any patient with an index date in June 2020).

**Figure 1. Study Design Schematic (Depiction for a Hypothetical Patient)**

AI = aromatase inhibitor; HER2- = human epidermal growth factor receptor 2-negative; HR+ = hormone receptor-positive; mBC = metastatic breast cancer.

Note: Figure not drawn to scale.

PFIZER CONFIDENTIAL

## 9.2 Setting

### 9.2.1 Inclusion Criteria

The following inclusion criteria will be applied:

1. De novo metastatic (stage IV) disease at initial breast cancer diagnosis during 2015-2019 (Howlader et al., 2018):
  - Incident breast cancer diagnosis will be identified using the SEER Site Recode 26000, which includes cases classified as “breast” according to the *International Classification of Diseases for Oncology, 3rd Edition codes*: C50.0-C50.9, excluding histology codes 9050-9055, 9140, and 9590-9992 (National Cancer Institute, 2023b).
  - Staging at diagnosis will be determined using criteria applicable during the specific period. Specifically, the American Joint Committee on Cancer (AJCC) staging 7th edition variable will be used to classify diagnoses in year 2015, the derived SEER combined stage group variable will be used to classify diagnoses in years 2016-2017, and the derived Extent of Disease (EOD) stage group variable will be used to classify diagnoses in years 2018-2019.
2. Age  $\geq$  65 years at diagnosis
3. “Age” as the reason for Medicare entitlement
4. Breast cancer recorded as the first cancer (coded as tumor sequence “1”) or the only cancer (coded as tumor sequence “0”) confirming no evidence of another, previous primary cancer diagnosis.
5. HR+/HER2- molecular subtype at diagnosis, using the SEER breast subtype variable (defined according to estrogen receptor [ER]/progesterone receptor [PR] and HER2 status)
6. Initiated 1L systemic therapy with a CDK4/6 inhibitor + AI or AI alone
  - Subsequently, and differing from Goyal et al. (2023), to assess the primary objective, the study cohort will be restricted to patients initiating 1L therapy with palbociclib + AI or AI alone within 6 months of mBC diagnosis:
    - It is assumed that most patients will initiate a systemic treatment within a few months of the diagnosis, and those who did not receive treatment within 6 months may have meaningful unobserved characteristics that likely influenced their treatment decisions.

PFIZER CONFIDENTIAL

7. To ensure complete data for identifying the 1L of therapy, patients will be required to have continuous enrollment in Medicare Parts A and B and have prescription drug coverage (Part D) with no HMO participation from date of diagnosis until they initiate the 1L therapy, and they are allowed up to 6 months to initiate first-line therapy.
8. Continuously enrolled in Medicare Parts A and B with no HMO participation for  $\geq$  6 months *before* the index date
  - Because HMOs are not obligated to provide information about healthcare encounters (i.e., administrative procedure and diagnosis codes) to the Medicare system, patients who were enrolled in an HMO during study period may have incomplete data on service utilization, which may affect the accuracy of measurement for comorbid conditions and receipt of systemic therapy lines.

### 9.2.2 Exclusion Criteria

Patients will be excluded if their mBC diagnosis was first recorded in a death certificate or at the time of autopsy.

## 9.3 Variables

All relevant study variables will be gathered or calculated from raw variables contained in the SEER-Medicare database. The following sections list and define the anticipated key analysis variables that will be collected or created from the study database. For covariates, categories may be further combined if appropriate for statistical purposes.

**Table 1. Study Outcomes and Stratification Variables with Associated Definitions**

Variable name	Type	Definition/categories
Outcome variables		
Overall survival	Outcome (primary objective)	Time in months from the study index date to all-cause death
CCI		

PFIZER CONFIDENTIAL

Variable name	Type	Definition/categories
CCI		
Time to chemotherapy	Outcome (exploratory objective)	Time in months from the study index date to first initiation of chemotherapy in any subsequent therapy lines
Exposure variable		
1L Treatment type	Exposure (primary objective)	
Patients initiating 1L therapy with one of the following regimens (to be identified in the Prescription Drug Event file using the generic drug names and HCPCS procedure codes, as applicable):
 
 
• Palbociclib + AI
 
• AI alone
 
 
AI will include the following individual agents:
 
 
• Anastrozole (HCPCS code: S0170)
 
• Letrozole (HCPCS code: N/A)
 
• Exemestane (HCPCS code: S0156)
 
 
Therapy line definition: For each patient, the 1L therapy will be defined as all agents administered within a 60-day period after treatment initiation. The 1L therapy will start on the date the first agent will be administered (or filled) and will be considered to have ended upon occurrence of the earliest of any of the following: treatment switch to a new regimen or a gap of more than 90 days in administration or refill of any of the 1L regimen drugs. The start and end dates of the second and subsequent therapy lines will be defined in a similar fashion. The rules

PFIZER CONFIDENTIAL

Variable name	Type	Definition/categories
		defining “treatment switch to a new regimen” are presented in Annex 2 .
Subsequent treatment	Exposure (exploratory objective)	All subsequent treatment lines for patients initiating 1L therapy with palbociclib + AI or AI alone, including a description of treatment switch from AI alone to palbociclib + AI.
Control variables or covariates		
Tumor grade at diagnosis	Clinical characteristic (assessed at mBC diagnosis)	
The tumor grade will be summarized as below:
 
 
• Grade 1 (lowest grade; well differentiated)
 
• Grade 2
 
• Grade 3
 
• Grade unknown
 

Metastatic site involvement at diagnosis	Clinical characteristic (assessed at mBC diagnosis)	
The SEER-defined metastatic site variables will be used to describe involvement of any of the following sites at diagnosis:
 
 
• Bone
 
• Brain
 
• Liver
 
• Lung
 
• An additional variable will be created to describe presence of visceral metastases using the composite of liver and lung.
 

National Cancer Institute's (NCI) Comorbidity Index (NCICI) Score	Clinical characteristic (assessed within the 6 months period before index date)	
The comorbidity burden during the 6-month baseline period will be assessed using the NCI's comorbidity index, which is described in the Klabunde adaptation of the Charlson Comorbidity Index, version 2021 (Klabunde et al., 2007; National Cancer Institute, 2023a). NCICI scores will be reported as continuous and categorical variables:
 
 
• Score 0
 
• <math>0 < \text{Score} \leq 1</math>
 
• <math>\text{Score} > 1</math>
 
 
The specific comorbidities represented in the NCICI include the following:
 
 
• Acute myocardial infarction
 

PFIZER CONFIDENTIAL

Variable name	Type	Definition/categories
		

• History of myocardial infarction

• Congestive heart failure

• Peripheral vascular disease

• Cerebrovascular disease

• Chronic obstructive pulmonary disease

• Dementia

• Paralysis (hemiplegia or paraplegia)

• Diabetes without complications

• Diabetes with complications

• Renal disease

• Mild liver disease

• Moderate/severe liver disease

• Peptic ulcer disease

• Rheumatologic disease

• AIDS

Age	Demographics (assessed at mBC diagnosis and at index date)	Age at diagnosis will be assessed as continuous and categorical variables (categories may be collapsed based on final sample size): 

• 65-69 years

• 70-74 years

• 75-79 years

• <math>\geq 80</math> years

Year of diagnosis	Demographics (assessed at mBC diagnosis)	Year of de novo mBC diagnosis will be described as a categorical variable: 

• 2015

• 2016

• 2017

• 2018

• 2019

PFIZER CONFIDENTIAL

Variable name	Type	Definition/categories
Race	Demographics (assessed at mBC diagnosis)	
Race will be defined using the SEER Race Recode variable and categorized as follows:
 
 
• American Indian/Alaska native
 
• Asian or Pacific Islander
 
• Black
 
• White
 
• Other or unknown
 
 
These categories may be further combined for statistical purposes as below:
 
 
• White
 
• Non-White
 

Origin/ethnicity	Demographics (assessed at mBC diagnosis)	
Ethnicity will be defined using the SEER Origin Recode variable defined by the NAACCR Hispanic Identification Algorithm (NHIA) and categorized as follows:
 
 
• Hispanic (Spanish-Hispanic-Latino)
 
• Non-Hispanic (non-Spanish-Hispanic-Latino)
 

Race-ethnicity	Demographics (assessed at mBC diagnosis)	
Race will be defined using the SEER Race Recode variable, and ethnicity will be defined using the SEER Origin Recode variable defined by the NAACCR Hispanic Identification Algorithm (NHIA) and categorized as follows:
 
 
• American Indian/Alaska native/unknown
 
• Hispanic
 
• Non-Hispanic Asian or Pacific Islander
 
• Non-Hispanic Black
 
• Non-Hispanic White
 

Marital status	Demographics (assessed at mBC diagnosis)	
Marital status will be categorized as follows:
 
 
• Married
 
• Not married 
 
○ Single (never married)
 
○ Unmarried living with domestic partner
 
○ Divorced
 
○ Separated
 
 
 

PFIZER CONFIDENTIAL

Variable name	Type	Definition/categories
		

○ Widowed

● Unknown

 
These categories may be further combined for statistical purposes as below:
 

● Single (never married)

● Married/unmarried living with domestic partner

● Divorced/separated/widowed

● Unknown

Geographic region	Demographics (assessed at mBC diagnosis)	
The geographic region of patients' county of residence will be defined according to the rural-urban continuum code (version year 2013) and categorized as follows:
 

● Big metro: Counties in metropolitan areas <math>\geq</math> 1 million population

● Metro: Counties in metropolitan areas of 250,000 to 1 million population

● Urban: Counties in metropolitan areas of <math><</math> 250,000 population

● Less urban: Nonmetropolitan counties adjacent to a metropolitan area

● Rural: Nonmetropolitan counties not adjacent to a metropolitan area

 
These categories may be further combined for statistical purposes as below:
 

● Large urban (big metro and metro areas)

● Small urban (urban and less urban areas)

● Rural

PFIZER CONFIDENTIAL

Variable name	Type	Definition/categories
Household income	Demographics (assessed using the latest available ACS data: 2008-2012)	The median household income based on patients' census tract of residence will be defined according to American Community Survey data (2008-2012). Data will be categorized using quartile distribution as follows: 
 
• Quartile 1 (e.g., < \$55,000)
 
• Quartile 2 (e.g., \$55,000-\$64,999)
 
• Quartile 3 (e.g., \$65,000-\$74,999)
 
• Quartile 4 (e.g., \$75,000+)
 
• Missing/unknown
 

LIS coverage	Demographics (assessed during 6 months before index date)	Patient's enrollment in an LIS plan during the 6-month baseline period will be assessed and summarized as a binary variable: 
 
• Any LIS coverage
 
• No LIS coverage
 

Medicaid (dual) eligibility	Demographics (assessed as available in the data at mBC diagnosis or treatment)	Medicare with Medicaid (dual) eligibility status will be summarized according to primary payer/insurance carrier at the time of initial diagnosis and/or treatment at the reporting facility: 
 
• Medicaid
 
• No Medicaid
 

1L = first line; 2L = second line; ACS = American Community Survey; AI = aromatase inhibitor; CDK4/6 = cyclin-dependent kinase 4 and 6; HCPCS = Healthcare Common Procedure Coding System; LIS = low-income subsidy; mBC = metastatic breast cancer; N/A = not applicable; NAACCR = North American Association of Central Cancer Registries; NCI = National Cancer Institute; NCICI = NCI Comorbidity Index; NHIA = NAACCR Hispanic Identification Algorithm; CCI [REDACTED]; SEER = Surveillance, Epidemiology, and End Results; CCI [REDACTED].

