### 9.7.1 Analyses of the Primary Objective

For the primary objective, the association between primary independent variable (treatment type: palbociclib + AI or AI alone) and the outcome variable (OS) will be assessed using unadjusted Kaplan-Meier analysis and an appropriate multivariable method. The primary method of analysis will be determined following an assessment of the balance in baseline characteristics between the 2 treatment groups. Specifically, we would explore the following methods: 1) multivariable Cox proportional hazards regression, 2) the inverse probability of treatment weighting (IPTW), and 3) propensity score matching (PSM). Both IPTW and PSM are propensity score (PS)-based methods commonly used to achieve balance between treatment and control groups in retrospective cohort study designs. The baseline covariates or control variables that will be considered for adjustment in the multivariable Cox proportional hazards (CPH) regression and in logistic regression for deriving treatment probabilities (i.e., PSs for IPTW and PSM) are described earlier in [Table 1](#). The multivariable CPH model will generate a hazard ratio, along with 95% CI, for each of the covariates included in the model, indicating higher or lower rate of death (relative to a reference category) at any given point in time following the index date. The final lists of variables to be used in the model will be discussed and determined during analysis development and will be recorded in the SAP prior to final analysis.

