Metastatic site involvement at diagnosis	Clinical characteristic (assessed at mBC diagnosis)	The SEER-defined metastatic site variables will be used to describe involvement of any of the following sites at diagnosis: 
 • Bone • Brain • Liver • Lung • An additional variable will be created to describe presence of visceral metastases using the composite of liver and lung.
NCI Comorbidity Index (NCICI) Score	Clinical characteristic (assessed within the 6 months period before index date)	The comorbidity burden during the 6-month baseline period will be assessed using the NCI's comorbidity index, which is described in the Klabunde adaptation of the Charlson Comorbidity Index, version 2021 (Klabunde et al., 2007; National Cancer Institute, 2023a). NCICI scores will be reported as continuous and categorical variables: 
 • Score 0 • $0 < \text{Score} \leq 1$ • $\text{Score} > 1$

PFIZER CONFIDENTIAL

CT24-WI-GL03-RF03 2.0 Non-Interventional Statistical Analysis Plan For Secondary Data Collection Study
 01-Jun-2020
 Page 13 of 29

Variable	Role/objective	Definition
		
The specific comorbidities represented in the NCICI include the following:
 
 • Acute myocardial infarction • History of myocardial infarction • Congestive heart failure • Peripheral vascular disease • Cerebrovascular disease • Chronic obstructive pulmonary disease • Dementia • Paralysis (hemiplegia or paraplegia) • Diabetes without complications • Diabetes with complications • Renal disease • Mild liver disease • Moderate/severe liver disease • Peptic ulcer disease • Rheumatologic disease • AIDS
Age	Demographics (assessed at mBC diagnosis and at index date)	
Age at diagnosis will be assessed as continuous and categorical variables:
 
 • 65-69 years • 70-74 years • 75-79 years • ≥ 80 years
Year of diagnosis	Demographics (assessed at mBC diagnosis)	
Year of de novo mBC diagnosis will be described as a categorical variable:
 
 • 2015 • 2016 • 2017 • 2018 • 2019

PFIZER CONFIDENTIAL

Variable	Role/objective	Definition

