7.2 STATISTICAL ANALYSES

7.3 ANALYSES FOR PRIMARY OBJECTIVE

For the primary objective, the association between primary independent variable (treatment type: palbociclib + AI or AI alone) and the outcome variable (OS) will be assessed using unadjusted Kaplan-Meier analysis and multivariable methods. The primary method of analysis to account for observed confounders will be stabilized inverse probability of treatment weighting (sIPTW). Additionally, as sensitivity analyses, multivariable Cox proportional hazards (CPH) regression and propensity score matching (PSM) will be performed. *Both IPTW and PSM are propensity score (PS)-based methods commonly used to achieve balance between treatment and control groups in retrospective cohort study designs.* All methods are described below in detail.

Kaplan-Meier Analysis

Time-to-event outcome (i.e., OS) will be described using unadjusted Kaplan-Meier analyses; median time-to-event (in months) and landmark probabilities of event at various timepoints (e.g., 12 months, 24 months) will be estimated, along with 95% CIs and log-rank *P* values. Graphical displays of the data will also be generated as appropriate. Kaplan-Meier analysis may also be performed using the stabilized weights or among the PS-matched groups (see details in this section below), and the weighted or PS-matched survival curves may be drawn.

Cox Proportional Hazards Regression

The CPH regression model may be used to estimate a hazard ratio of the OS, along with 95% CI, for the primary exposure—a dichotomous variable indicating whether the patient received AI + palbociclib versus AI alone—and for each of the control variables included in the model, indicating higher or lower rate of death (relative to a reference category) at any given point in time after the index date. The patient demographic and clinical characteristics that will be considered for confounding adjustment in the model are described earlier in [Table 5-2](#).

Propensity Score Estimation

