As the first step in implementation of PS-based methods (IPTW and PSM), the PS (i.e., the estimated probability of treatment assignment) will be obtained from a logistic regression model where the treatment assignment (treatment vs. control) will be regressed on a set of covariates or confounders. The baseline covariates or control variables that will be considered for adjustment in the multivariable logistic regression for deriving treatment probabilities (i.e., PSs for IPTW and PSM) are described earlier in [Table 5-2](#). The following variables will be included in the model: age group, race, year of mBC diagnosis, marital status, geographic status of residence, median household income, LIS coverage, tumor grade at initial diagnosis, involvement of metastatic sites at initial diagnosis (bone, brain, liver, and lung as independent binary variables), and NCICI score category. If any covariates are identified to have missing data, they may be coded as “missing” or “unknown” and included as categorical variables in the model.

Covariate Balancing

The following process will be implemented to determine whether there is sufficient overlap between the patient populations of the 2 treatment cohorts:

- Compute the standardized mean difference in PS for each level of each baseline covariate
- Graphically assess differences in the full distribution of each covariate between 2 treatment cohorts
- An absolute standardized mean difference < 0.1 indicates negligible difference and is considered a good balance

Covariate balance will be examined using both IPTW and PSM techniques as described below. Subsequently, depending on the quality of balance, the endpoint (OS) may be assessed using one or both techniques (Austin, 2014; Buchanan et al., 2014).

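### Comorbidity enters the primary propensity score, and its balance check, only as a three-level NCICI category, so single conditions can stay imbalanced unseen and can leave a small bias in the OS hazard ratio

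*Protocol*

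**What the plan says.** Protocol 9.7.1 leaves the final variable list to the SAP: it "will be recorded in the SAP prior to final analysis". SAP 7.3 (Propensity Score Estimation) then gives that list. Its clinical part ends with tumor grade and "involvement of metastatic sites at initial diagnosis (bone, brain, liver, and lung as independent binary variables), and NCICI score category". The four metastatic sites therefore enter one by one, while comorbidity enters as a single three-level variable: 0, above 0 up to 1, and above 1.

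Protocol Table 1 and SAP Table 5-2 also name 16 conditions, introduced by "The specific comorbidities represented in the NCICI include the following". They appear inside the NCICI row as parts of the index, not as covariates in their own right. On the score itself, Table 5-2 says "NCICI scores will be reported as continuous and categorical variables".

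For balance, SAP 7.3 says "Compute the standardized mean difference in PS for each level of each baseline covariate" and adds that "An absolute standardized mean difference < 0.1 indicates negligible difference and is considered a good balance". Adjustment for residual imbalance in the weighted Cox model is allowed but not required. Neither document asks for balance, or even a descriptive table, by single condition.

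**The concern.** Balancing a summed score does not balance its parts. Within one category the arms can hold different mixes, for example more dementia in the AI-alone arm offset by more diabetes in the palbociclib arm. If a condition both lowers the chance of receiving palbociclib and shortens survival, the weighted hazard ratio is pulled below 1, which is the direction of the superiority hypothesis in SAP section 3.

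The planned safeguards share the blind spot. The balance table is organised by covariate level. The optional residual adjustment can only follow an imbalance that someone has looked at. Matching uses the same propensity score. The Cox sensitivity model draws on Table 5-2, where the NCICI score is the only comorbidity variable. Agreement among the three methods would therefore say little about single conditions. Protocol 9.7.1 adds weight to the balance check, because it lets the estimate be read as the true effect if no significant baseline differences are seen.

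Unlike performance status, which Protocol 9.9 lists as unobserved, these conditions must be identified from claims to compute the index at all.

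**Working it through.** The documents state no sample size, event count, comorbidity prevalence or index weights, so there is no figure of the plan's to reproduce. Every input below is an assumption, except the follow-up range: 1 February 2015 to 31 December 2020 is 71 months, and 30 June 2020 to 31 December 2020 is 6 months.

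**1. One residual imbalance, by formula.** For a binary condition with weighted prevalence p1 (palbociclib) and p0 (AI alone) and death hazard ratio h, the bias factor is approximately (1 + p1(h − 1)) / (1 + p0(h − 1)).
- 1% vs 3%, h = 1.5: 1.005 / 1.015 = 0.990
- 2% vs 6%, h = 2.0: 1.02 / 1.06 = 0.962
- 5% vs 15%, h = 3.0: 1.10 / 1.30 = 0.846

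**2. Simulation of 1,000,000 patients, true hazard ratio 1.** Prevalence and death hazard ratio were: dementia 6%, 2.0; heart failure 12%, 1.8; COPD 15%, 1.4; diabetes 25%, 1.2; renal disease 10%, 1.5; peripheral vascular disease 8%, 1.2. Baseline median OS was 40 months, with uniform censoring at 6 to 71 months. Three selection patterns were used:
- mild: log-odds of palbociclib −0.7 for dementia, −0.3 for heart failure, −0.2 each for COPD and renal disease
- strong: −1.4, −0.7, then −0.3 for COPD and −0.4 for renal disease
- proportional: −0.6 × ln(h)/ln 2 for every condition

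Score weights were either 1 for each condition (unit) or ln(h)/ln 2 (prognostic). The columns give the sIPTW Cox hazard ratio.

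| Selection, score weights | No adjustment | Category only | Dementia SMD, category only | Category + flags |
|---|---|---|---|---|
| mild, unit | 0.945 | 0.979 | −0.120 | 1.001 |
| strong, unit | 0.899 | 0.957 | −0.225 | 1.000 |
| proportional, unit | 0.922 | 0.979 | −0.078 | 1.000 |
| mild, prognostic | 0.945 | 0.985 | −0.101 | 1.001 |
| strong, prognostic | 0.905 | 0.976 | −0.191 | 1.006 |
| proportional, prognostic | 0.923 | 0.985 | −0.051 | 1.001 |

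With the category alone, the SMDs of the three NCICI levels were 0.00 throughout, yet dementia passed the 0.1 limit in four of six settings. Heart failure ran from −0.01 to −0.12 and diabetes from +0.04 to +0.14. With flags added, the SMDs for dementia, heart failure and diabetes were 0.00. The bias from the category alone is 1 − 0.985 = 1.5% to 1 − 0.957 = 4.3%. The share already removed by the category runs from 1 − 0.043/0.101 = 57% to 1 − 0.015/0.077, about 80%.

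**3. Other simulations, true hazard ratio 1.** One used 400,000 patients per scenario and eight conditions, including dementia 7% (odds ratio 0.30 for palbociclib, death hazard ratio 2.0) and heart failure 9% (0.6, 1.6). The category gave 0.96-0.98 with dementia SMD −0.06 to −0.21; individual indicators in place of the score gave 0.996-0.999 with SMD 0.00. Another also put age and low-income subsidy in the propensity score. The category gave 0.97-0.99 with dementia SMD −0.11 to −0.18; adding flags gave about 1.00 and 0.00.

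**4. Precision.** In 500 replicates with the eight-condition set-up, the empirical standard error (category vs indicators) was 0.0944 vs 0.0961 at n = 900 (ratio 1.018) and 0.0674 vs 0.0684 at n = 1,500 (ratio 1.015). With age and low-income subsidy in the model, adding flags changed it by under about 3%.

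**The case against.** The strongest reply is that this is a modelling choice, not an error. The plan adjusts for a cited comorbidity index built for cancer claims data and lists its propensity variables in advance. That stands, and it is why the index should stay in the model.

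It is also fair that the size rests on invented inputs. The index weights are not in the documents, and the bounds of the middle category suggest non-integer, condition-specific weights, so we cannot tell which conditions share a level. Age, low-income subsidy and other listed covariates may absorb part of the imbalance; with age and subsidy included, the bias was 1-3%. Imbalances can also offset one another, as diabetes did. On the log scale the bias is about 0.020/0.0944 = 0.2 to 0.041/0.0674 = 0.6 of a standard error at the assumed sample sizes. All this limits the claim to a small, possible bias.

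Some mitigation exists. The Cox list is not closed, the score is also reported as continuous, and residual adjustment is permitted. None of these requires anyone to look at a single condition, so the gap in the balance check remains.

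A reader might infer two stronger things. One is that the primary hazard ratio will be confounded in favour of palbociclib. The documents show no imbalance and no selection pattern, so they support only that it can be. The other is that the index should be replaced by its components, which Table 1 already provides. Table 1 lists them as parts of the index, and the documents do not show that replacement would do better; pooling rare conditions into one indicator would also bring back the summing problem.

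**Conclusion.** The point holds as a gap in the balance check with a small possible effect on the estimate. As SAP 7.3 is written, a single condition can breach the plan's own 0.1 limit while every comorbidity row passes. Under the assumptions shown, the residual bias is about 1-4% toward palbociclib, after the category has already removed most of the simulated comorbidity confounding.

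The direction depends on conditions that both discourage palbociclib and shorten survival; the size depends on prevalences, selection odds and index weights that the documents do not give. At its upper end the bias is about as large as the PALOMA-2 effect cited in both documents (hazard ratio 0.956), but it is small beside the observational estimates they cite (0.76 and 0.59). It is worth closing because the information has to be derived anyway.

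**What to change.** In SAP 7.3:
- Keep the NCICI category in the propensity score.
- Add the component conditions with adequate counts to the SMD table, before adjustment, after weighting and after matching, under the existing 0.1 limit. State the minimum count before any outcome comparison is run; the documents give no cohort size from which to derive one.
- Where a condition's absolute SMD is 0.1 or more, require that its indicator be added to the propensity model or adjusted for in the weighted Cox model. Name one route in advance. The first keeps the hazard ratio marginal.
- Add a sensitivity analysis with the NCICI category plus indicators for the sufficiently common conditions.
- Report sparse conditions, possibly AIDS or paralysis, descriptively only.

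The cost is SAP wording, a longer balance table, a few more model terms and a standard error about 1-3% larger in simulation. The full propensity model has more terms than those simulated and the cohort size is unknown, so the weight distribution should be inspected after any indicator is added.
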